## Subject Selection

- A. Inclusion criteria:
  - Healthy volunteers between 18 and 70 years of age
- B. Exclusion criteria:
  - Age less than 18 years.
  - The presence of any significant medical condition that might significantly confound the collection of biological data in the study including cancer, diabetes, IBD, Advanced Renal Disease, Nut Allergy
  - Unwilling to follow protocol

- Participation in another interventional clinical trial.
- Prisoners, pregnancy, or direct employees of the investigative team.

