#### 6. Research Plan

Overview: Using targeted assays of mitochondrial energetics, 10X genomics, and the microbiome, we will assess changes in skeletal muscle bioenergetics and the leukocyte transcriptome induced by a prescribed 96-hour protein restriction diet, tracking the impact of these changes on the dynamic response patterns of these parameters in healthy control patients.

Study Time points Summary							
	Days -7 to -1	Baseline/Day 0	Day 2	Day 4	Day 7	Day 14	
Consent	x						
Paffenbarger IQ	х						
IPR Study IQ		х	х	х	х	х	
Stool Kit Distribution	x	х	х				
Diet Kit Distribution		х	х				
Blood		х	х	х	х	х	
Urine		х	х	х	х	х	
Feces		х		х	х		
Cheek Swab		х	х	х	х	Х	
Muscle Biopsy		х		х	х		
Meal Logger				Days 5 thru 14			

Health Questionnaires: We will collect height and weight information to be utilized in the diet equation, as well as 2 questionnaires. The first is a physical activity Paffenbarger questionnaire which is used for the diet equation (see below) and an IPR study questionnaire to track energy level, mental awareness, and digestive issues.

Diet Modification: Subjects will follow a 4 day protein restricted diet using Scandishake® mixed with almond milk which will be provided. They may also drink water. No food, other beverages, or alcohol may be consumed. The amount of diet to be consumed will be calculated for each patient based upon resting energy expenditures plus additional energy needs using the Paffenberger IQ. REE = 9.99 x weight (KG) + 6.25 x height (cm) - 4.92 x age + 166 x sex (males, 1; females, 0) - 161. Patients will receive the study diet (ScandiShake® [any of 4 flavors] mixed

with almond milk), calculated individually for a total daily volume to achieve 30% caloric restriction and 70% protein restriction. These will be consumed by the study subjects at home in an unrestricted manner, in that they may be consumed at any point of time in the day.

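### Pregnancy is excluded but breast-feeding is not, and the diet calculation has no term for milk production, so a breast-feeding volunteer would be restricted by more than the stated 30%

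*Protocol*

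**What the plan says.** **Eligibility (Protocol, Subject Selection).** The inclusion criterion is "Healthy volunteers between 18 and 70 years of age", with no limit on sex. The only exclusion that touches reproductive status is "Prisoners, pregnancy, or direct employees of the investigative team". A separate exclusion covers "The presence of any significant medical condition that might significantly confound the collection of biological data" and gives as examples cancer, diabetes, inflammatory bowel disease, advanced renal disease and nut allergy. Breast-feeding is not mentioned.

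**Diet amount (Protocol, section 6, Research Plan).** Resting energy expenditure (REE) comes from a formula that begins "REE = 9.99 x weight (KG) + 6.25 x height (cm) - 4.92 x age + 166 x sex" (1 for males, 0 for females) and ends with a constant of -161. The amount of diet is "based upon resting energy expenditures plus additional energy needs using the Paffenberger IQ". The same section explains that questionnaire: "The first is a physical activity Paffenbarger questionnaire which is used for the diet equation". The daily volume is then set for each subject to give 30% caloric and 70% protein restriction over 4 days. Water is allowed. Beyond that, "No food, other beverages, or alcohol may be consumed".

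**Size and benefit.** Subject Enrollment anticipates 10 subjects. Section 8 states that taking part brings subjects no additional benefit.

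**The concern.** The eligibility list and the diet calculation do not fit together for one kind of volunteer. A healthy breast-feeding woman meets the inclusion criterion and no exclusion names her. The calculation that fixes her intake counts resting expenditure and physical activity only. Energy used to produce milk enters neither part, and the diet rules leave no other source of energy for the 4 days. The 30% that the plan sets out to achieve would therefore not be the restriction she undergoes.

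Two things are at stake. One is subject protection: a volunteer who gains nothing from the study would be restricted more than the protocol states. The other is uniformity of exposure. The study means to describe the response to one defined restriction and to use it as a benchmark for a later surgical study. In a sample of 10, one subject on a deeper restriction is 1/10 = 10% of the data.

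**Working it through.** **Inputs from the protocol**
- REE = 9.99 × weight (kg) + 6.25 × height (cm) - 4.92 × age + 166 × sex - 161, with sex = 0 for a woman.
- Estimated need E = REE + additional need from the activity questionnaire.
- Caloric restriction 30%, so energy supplied S = 0.70 × E.
- No other energy source on diet days.

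**Inputs not in the protocol (all assumptions)**
- A woman of 65 kg, 165 cm and 30 years.
- Activity of 300 kcal/day.
- Energy cost of milk, L, from 100 to 500 kcal/day. The low end stands for cases such as partial breast-feeding.
- The 30% is read as relative to total daily need, since the protocol gives no other reference.

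**The plan's own figure.** The protocol gives no worked example, so the 30% can be checked only as a target. With L = 0, restriction = 1 - 0.70E/E = 30.0%, as intended.

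**Restriction when milk has an energy cost.** Actual need is E + L while supply stays at 0.70E, so

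restriction = 1 - 0.70E/(E + L) = 0.30 + 0.70 × L/(E + L).

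The last term is positive for every L > 0. The direction therefore needs no outside figure.

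**Example**
- REE = 9.99 × 65 + 6.25 × 165 - 4.92 × 30 - 161 = 649.35 + 1,031.25 - 147.60 - 161 = 1,372 kcal.
- E = 1,372 + 300 = 1,672 kcal.
- S = 0.70 × 1,672 = 1,170 kcal.

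| L (kcal/day) | Need E + L (kcal) | Restriction |
|---|---|---|
| 0 | 1,672 | 30.0% |
| 100 | 1,772 | 34.0% |
| 200 | 1,872 | 37.5% |
| 300 | 1,972 | 40.6% |
| 400 | 2,072 | 43.5% |
| 500 | 2,172 | 46.1% |

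**Sensitivity.** Four assumed women (55 to 85 kg, 160 to 170 cm, 25 to 40 years) with activity of 0, 300 or 600 kcal/day give 33.1% to 35.1% at L = 100, 38.6% to 43.4% at L = 300, and 43.2% to 49.8% at L = 500. Body size and activity change the result by a few points; the assumed milk energy changes it most.

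**The case against.** The strongest reply is that this is an omission, not an error. The protocol states a target, says nothing about breast-feeding volunteers, and contains no two statements that conflict. Any need that a predictive equation misses would move a subject off exactly 30%. That is fair, and a reader who inferred that the protocol contradicts itself, or that its 30% is wrong for the subjects it expects, would go too far. What remains is that the gap is specific and foreseeable, in a list that already names pregnancy.

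A second reply is that other safeguards would catch the case: entry is limited to healthy volunteers, the list of medical conditions may not be exhaustive, and staff meet each volunteer before consent. These make it less likely that such a woman would be enrolled unnoticed. They do not close the gap, because breast-feeding in a healthy woman does not fit the wording or the examples of the medical-condition criterion. The consent form might mention it, but that would not alter the eligibility list.

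A third reply is that the case is improbable among 10 subjects aged 18 to 70, and that the effect on the analysis is small. This is a single-arm exploratory pilot, so there is no comparison of arms to bias, and the microbiome response is measured as change from baseline. This also stands. Change from baseline does not, however, equalise the restriction that produces the change.

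Two stronger readings are tempting. One is that the restriction would be some 40% to 47%. That range needs milk energy of 300 to 500 kcal/day and activity of 200 to 400 kcal/day, none of which the protocol gives, and it leaves out lower milk costs. The other is that the infant would be exposed to the restriction. The infant does not take the study diet, and the protocol contains nothing on milk supply or infant outcomes.

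**Conclusion.** The point holds as a minor, conditional one. As written, the criteria do not exclude a breast-feeding volunteer, and the diet calculation would restrict her by more than 30% of actual need for any milk energy cost above zero. That direction follows from the protocol's own formula and its ban on other food, given that the 30% refers to total daily need.

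The size does not follow from the protocol. In the assumed example it runs from about 34% at 100 kcal/day to 41% at 300 and 46% at 500, and these figures only illustrate how far the departure could go. The situation may never occur. If it did, one subject in 10 would have had a deeper restriction than the protocol describes, in a study that offers her no benefit.

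**What to change.** Add breast-feeding beside pregnancy in the exclusion list under Subject Selection, and ask about it at the screening visit. Eligibility would then be consistent with the diet calculation. No change to the diet, its equation or its rules is proposed.

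The cost is one added word in the criteria and one screening question. The downside is the loss of at most a very few volunteers.

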# Subject Enrollment

We anticipate enrolling 10 patients for up to a year following study initiation. Patients who express interest in learning more about the study will meet with a member of the study staff who will describe the study, review the informed consent form, give them a copy of the informed consent to read and answer any questions. Potential participants will be allowed to take a copy of the consent form, as well as written information about the study if they so desire. When possible, signing of the consent shall occur at least one day prior to diet initiation to allow adequate time for patient to make consideration without any stress. Any questions will be answered by the Principal Investigator or other study team members.

# **Compensation**

The study payment and time schedule:

Baseline Visit	(1-1.5 hours)	\$100.00
Day 2 Visit	(30-40 minutes)	\$ 50.00
Day 4 Visit	(1 hour)	\$100.00
Day 7 Visit	(1 hour)	\$100.00
Day 14 Visit	(1-1.5 hours)	\$150.00
Total		\$500.00

Statistical Analysis This will be performed in a blinded fashion (no patient identifiers) by the UF Surgery Department Statistical Support Group.

## 7. Possible Discomforts and Risks:

Microbiopsy: There is a small risk of muscle damage, infection, or prolonged bleeding but these are very rare. Subjects may experience muscle soreness and bruising at the biopsy site. No sutures are required to heal the puncture but they will be left with a small scar at the puncture site.

Blood draw: The risks of drawing blood from a vein include discomfort at the site of puncture; possible bruising and swelling around the puncture site; rarely an infection; and, uncommonly, faintness from the procedure.

Protein Restrictive Diet: Subjects may experience a change in bowel habits, constipation, loose stool and cramping and possible weight loss. Subjects may experience a change in energy level during the 4 days of the protein restricted diet.

#### 8. Possible Benefits:

Participation in this research will not provide any additional benefits to the subjects. Our hope is that discoveries from this study will eventually lead to a better understanding of how nutritional interventions may improve the probability of successful outcomes following open AAA surgery.

## 9. Conflict of Interest:

No conflict of interest exists for this project.

